#### **5.4.3.3 Congenital Anomalies/Birth Defects and Abortions**

Any congenital anomaly/birth defect in a child born to a female patient exposed to study drug or the female partner of a male patient exposed to study drug should be classified as a serious adverse event, recorded on the Adverse Event eCRF, and reported to the Sponsor immediately (i.e., no more than 24 hours after learning of the event; see Section 5.4.2). Any abortion should be reported in the same fashion (as the Sponsor considers abortions to be medically significant).

### **5.5 FOLLOW-UP OF PATIENTS AFTER ADVERSE EVENTS**

#### **5.5.1 Investigator Follow-Up**

The investigator should follow each adverse event until the event has resolved to baseline grade or better, the event is assessed as stable by the investigator, the patient is lost to follow-up, or the patient withdraws consent. Every effort should be made to follow all serious adverse events considered to be related to study drug or trial-related procedures until a final outcome can be reported.

During the study period, resolution of adverse events (with dates) should be documented on the Adverse Event eCRF and in the patient's medical record to facilitate source data verification.

All pregnancies reported during the study should be followed until pregnancy outcome.

### **5.5.2 Sponsor Follow-Up**

For serious adverse events, adverse events of special interest, and pregnancies, the Sponsor or a designee may follow up by telephone, fax, electronic mail, and/or a monitoring visit to obtain additional case details and outcome information (e.g., from hospital discharge summaries, consultant reports, autopsy reports) in order to perform an independent medical assessment of the reported case.

### **5.6 ADVERSE EVENTS THAT OCCUR AFTER THE ADVERSE EVENT REPORTING PERIOD**

The Sponsor should be notified if the investigator becomes aware of any serious adverse event that occurs after the end of the adverse event reporting period (defined as 8 weeks after the last dose of study drug the patients receives, either in this study or an OLE, if initiated), if the event is believed to be related to prior study drug treatment. These events should be reported through use of the Adverse Event eCRF. However, if the EDC system is not available, the investigator should report these events directly to the Sponsor or its designee, either by faxing or by scanning and emailing the Serious Adverse Event/Adverse Event of Special Interest Reporting Form using the fax number or email address provided to investigators.

### **5.7 EXPEDITED REPORTING TO HEALTH AUTHORITIES, INVESTIGATORS, INSTITUTIONAL REVIEW BOARDS, AND ETHICS COMMITTEES**

The Sponsor will promptly evaluate all serious adverse events and adverse events of special interest against cumulative product experience to identify and expeditiously communicate possible new safety findings to investigators, IRBs, ECs, and applicable health authorities based on applicable legislation.

To determine reporting requirements for single adverse event cases, the Sponsor will assess the expectedness of these events using the GDC-0853 Investigator's Brochure.

The Sponsor will compare the severity of each event and the cumulative event frequency reported for the study with the severity and frequency reported in the applicable reference document.

Reporting requirements will also be based on the investigator's assessment of causality and seriousness, with allowance for upgrading by the Sponsor as needed.

An unblinded IMC and Scientific Oversight Committee will monitor the incidence of adverse events during the study. An aggregate report of any clinically relevant imbalances that do not favor the test product will be submitted to health authorities.

## **6. STATISTICAL CONSIDERATIONS AND ANALYSIS PLAN**

Details of all statistical methods (including scoring of disease-activity or PRO instruments and missing data handling) will be provided in the Data Analysis Plan (DAP).

### **6.1 DETERMINATION OF SAMPLE SIZE**

The purpose of this study is estimation and hypothesis generation regarding the effect of GDC-0853 on Week 48 SRI-4 response rate relative to placebo in moderate to severe active SLE patients and a biomarker-defined subgroup of patients. A total of 240 patients will be randomly allocated in a 1:1:1 ratio to receive one of two doses of GDC-0853 (200 mg BID GDC-0853 [Arm A] or 150 mg QD GDC-0853 [Arm B]) or placebo (Arm C). This sample size will provide approximately 88% power at a 2-sided 0.05 significance *level* to detect a 25% absolute improvement in the response rate for a GDC-0853 containing arm relative to the placebo arm assuming a placebo response-rate of 50%. Patients without post-baseline response assessments will be treated as non-responders. For an evaluation of efficacy in a subgroup defined by a predictive biomarker with 50% prevalence, the total sample-size of 80 patients per arm provides approximately 80% power to detect a 25% improvement with *2-sided* 0.20 *significance level*, using the Fisher's Exact Test. No adjustment for multiple comparisons will be made.

### **6.2 SUMMARIES OF CONDUCT OF STUDY**

The final analysis will be based upon patient data collected through patient discontinuation or study discontinuation, whichever occurs first. The number of patients who enroll, discontinue, or complete the study will be summarized. Reasons for premature study withdrawal will be listed and summarized. Enrollment and major protocol deviations will be listed and evaluated for their potential effects on the interpretation of study results. All summaries will be presented according to randomized treatment assignment.

### **6.3 SUMMARIES OF TREATMENT GROUP COMPARABILITY**

Treatment group comparability will be analyzed. Demographic and baseline characteristics such as age, sex, weight, and disease activity will be summarized by treatment group. For categorical variables, the descriptive statistics will include counts and proportions. For continuous variables, the descriptive statistics will include the number of observations, mean, standard deviation, median, minimum, and maximum values.

## 6.4 EFFICACY ANALYSES

Efficacy analysis will be conducted for the intent-to-treat population, defined as all randomly allocated patients. Sensitivity analyses of additional study population (e.g., completers, *or* per protocol [excluding major protocol violators]) may also be performed *for the primary endpoint or key secondary endpoints* and will be detailed in the DAP. Biomarker-defined subgroup analyses will also be performed to identify subsets of patients who derive enhanced clinical benefit from GDC-0583. The focus of the subgroup efficacy analyses is on, but not limited to, subgroups defined by plasmablast signature levels.

Statistical tests will be conducted at the 0.05 significance level for the intent-to-treat (ITT) population and at the 0.20 significance level for plasmablast-signature defined subgroups. No multiplicity adjustments will be made to control the overall Type I error, and positive tests will be viewed as hypothesis generating rather than confirmatory.

### 6.4.1 Primary Efficacy Endpoint

The primary efficacy *endpoint* for this study is SRI-4 response at Week 48.

*The primary endpoint will be compared between each of the two GDC-0853 arms and the placebo arm by using the Cochran-Mantel-Haenszel test statistic, stratified by the factors used at randomization. The absolute difference in remission rates and 95% CI for the point estimate will be provided.*

### 6.4.2 Secondary Efficacy Endpoints

The secondary efficacy endpoints *for this study* are as follows:

- *SRI-4 response at Week 48 with a sustained reduction of OCS dose to < 10 mg/day and ≤ Day 1 dose during Week 36 through Week 48*
- *SRI-4 response at Week 24 with a sustained reduction of OCS dose to < 10 mg/day and ≤ Day 1 dose during Week 12 through Week 24*
- *SRI-4 response at Week 24*
- *SRI-6 response at Weeks 24 and 48*
- *BICLA response at Weeks 24 and 48*
- *SRI-4 response at Week 48 in patients with high plasmablast signature levels relative to patients with low levels*
- *SRI-4 response at Week 48 with a sustained reduction of OCS dose to < 10 mg/day and ≤ Day 1 dose during Week 36 through Week 48 in patients with high plasmablast signature levels relative to patients with low levels*

*The secondary endpoints will be analyzed in the same fashion as the primary endpoint.*

*Further details for the secondary efficacy analyses will be specified in the DAP.*

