### **1.2.2 Nonclinical Experience with GDC-0853**

GDC-0853 is a highly selective, orally administered, reversible inhibitor of BTK that is being developed by Genentech, Inc. as a potential therapeutic for autoimmune diseases,

including rheumatoid arthritis (RA) and SLE. GDC-0853 has undergone extensive investigation in nonclinical in vitro and in vivo studies to characterize its pharmacological, metabolic, and toxicological properties (see the GDC-0853 Investigator's Brochure).

In vitro cell-based experiments suggest that antagonism of BTK leads to inhibition of BCR-dependent cell proliferation and a reduction of inflammatory cytokine production from myeloid cells (including tumor necrosis factor alpha [TNF- $\alpha$ ], interleukin [IL]-1, and IL-6) by preventing signaling through the Fc $\gamma$ RIII receptor (di Paolo et al. 2011; Liu et al. 2011). GDC-0853 effectively blocks BCR- and CD40-mediated activation and proliferation of B cells. BTK in B cells also plays a role in TLR4-mediated B-cell proliferation and class switching. In monocytes, GDC-0853 inhibits TLR4- and immune complex-mediated inflammatory cytokine production, including TNF- $\alpha$ , which contributes to disease pathogenesis in SLE (Mina-Osorio et al. 2013; Bender et al. 2016). In dendritic cells, BTK contributes to TLR8-mediated cytokine production (TNF- $\alpha$  and IL-6) (Sochorová et al. 2007). In basophils, BTK-dependent activation of the Fc $\epsilon$ R leads to activation and up-regulation of CD63. In addition, GDC-0853 has been shown to inhibit the differentiation of human plasmablasts into plasma cells in vitro (see the GDC-0853 Investigator's Brochure). Patients with lupus have multiple abnormalities in the blood, including increased levels of plasmablasts (Anolik et al. 2004). Together, these data suggest that lupus patients with elevated levels of plasmablasts might demonstrate a more robust clinical response to GDC-0853. Therefore, an RNA signature biomarker encompassing genes preferentially expressed in plasmablasts was developed to detect the presence of elevated plasmablasts in the peripheral blood. In addition, efficacy in patients with high or low levels of the plasmablast signature will be compared for potential increased or decreased efficacy, respectively (see Table 1).

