**Table 1 Objectives and Corresponding Endpoints**

Objectives	Corresponding Endpoints
Primary Efficacy Objective:	

 
To evaluate the clinical efficacy of GDC-0853 in combination with SOC
 
	
 
SRI-4 response at Week 48
 

Secondary Efficacy Objectives:	

 
To evaluate the clinical efficacy of GDC-0853 over time using the SRI-4 as a standardized disease activity measure
 
	
 
SRI-4 response at Week 48 with a sustained reduction of OCS dose to < 10 mg/day and ≤ Day 1 dose during Week 36 through Week 48
 
SRI-4 response at Week 24 with a sustained reduction of OCS dose to < 10 mg/day and ≤ Day 1 dose during Week 12 through Week 24
 
SRI-4 response at Week 24
 

 
To evaluate if patients with high plasmablast signature levels have an enhanced clinical response to GDC-0853 relative to patients with low levels
 
	
 
SRI-4 response at Week 48
 
SRI-4 response at Week 48 with a sustained reduction of OCS dose to < 10 mg/day and ≤ Day 1 dose during Week 36 through Week 48
 

 
To evaluate the clinical efficacy of GDC-0853 over time using BICLA and SRI-6 as standardized disease activity measures
 
	
 
SRI-6 response at Weeks 24 and 48
 
BICLA response at Weeks 24 and 48
 

Exploratory Efficacy Objectives:	

 
To evaluate the clinical efficacy of GDC-0853 over time with multiple standardized disease activity measures
 
	
 
SRI-5, 7, and 8 response at Week 48
 
SRI-5-8 response at Week 48 with a sustained reduction of OCS dose to < 10 mg/day and ≤ Day 1 dose during Week 36 through Week 48
 
SRI-5, 7, and 8 response at Week 24
 
SRI-5-8 response at Week 24 with a sustained reduction of OCS dose to < 10 mg/day and ≤ Day 1 dose during Week 12 through Week 24
 

 
To evaluate the ability of GDC-0853 to prolong the time to first SLE flare
 
	
 
Time to first SLE Flare as defined by the SFI
 
Time to first SLE Flare as defined by the BILAG
 

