### **3.3.4 Rationale for Biomarker Assessments**

*Diagnostic* biomarker assessments aim to identify a biomarker that predicts response to GDC0853, which would be valuable to patients and treating physicians as an aid in identifying patients with increased likelihood to achieve clinical benefit, thus guiding treatment decisions. *In addition, at various timepoints after treatment, pharmacodynamic* biomarker samples will be collected and used to advance the understanding of the mechanism of action of GDC-0853 and define PK/PD relationships in SLE patients aiding in dose evaluation in this study as well as dose-regimen selection for future studies (see [Appendix 2](#)).

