### **3.3.6.5 Stratification**

Randomization will be stratified by disease activity based on the SLEDAI-2K score, entry dose of OCS, and geographic region obtained at screening.

Levels of baseline disease activity (SLEDAI-2K score) and corticosteroid use as well as geographic region independently impact a patient's ability to achieve response on the primary efficacy endpoint. Specifically, a reduction of  $\geq 4$  points in the SLEDAI-2K must be achieved to be classified as a responder. In addition, use of corticosteroids in SLE clinical trials can confound efficacy measurements and decrease the ability to detect the

biologic activity/efficacy of the experimental drug. For this reason, it is important to prevent treatment imbalances in these factors at baseline and thus randomization will be stratified by both SLEDAI-2K score ( $\geq 10$  or  $< 10$ ) and baseline corticosteroid use. Geographic region was chosen as the third strata, because regional variations in the management of SLE can manifest as variability in response rates, including differences in placebo rates (Kalunian et al. 2016; Khamashta et al. 2016). The stratification is intended to balance the proportion of patients from different regions across the study arms in order to limit any confounding of the study results.

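### The plasmablast objective asks whether the GDC-0853 effect is larger in high- than in low-signature patients, but the only method the protocol assigns does not estimate or test that difference

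*Combined protocol and SAP*

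**What the plan says.** The question is stated in several places. Table 1 gives the secondary objective: "To evaluate if patients with high plasmablast signature levels have an enhanced clinical response to GDC-0853 relative to patients with low levels". Section 6.4.2 lists the matching endpoint as "SRI-4 response at Week 48 in patients with high plasmablast signature levels relative to patients with low levels", and a second endpoint adds the oral corticosteroid (OCS) condition. Section 1.2.2 says that "efficacy in patients with high or low levels of the plasmablast signature will be compared for potential increased or decreased efficacy". Section 6.4.3 repeats both endpoints at Week 24 as exploratory.

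The method is stated once for the secondary endpoints, in Section 6.4.2: "The secondary endpoints will be analyzed in the same fashion as the primary endpoint". The primary method in Section 6.4.1 is a CMH test of each GDC-0853 arm against placebo, stratified by the randomization factors, with the absolute difference in rates and a 95% interval. Section 3.3.6.5 gives those factors: "Randomization will be stratified by disease activity based on the SLEDAI-2K score, entry dose of OCS, and geographic region obtained at screening". The signature is not among them. Section 6.4 sets the level for tests in signature-defined subgroups at 0.20.

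Section 6.1 gives about 80% power for a 25-point improvement in a biomarker subgroup of 50% prevalence, using Fisher's exact test at two-sided 0.20. The study is described as estimation and hypothesis generating, with no multiplicity control. Section 6.4.2 ends: "Further details for the secondary efficacy analyses will be specified in the DAP".

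**The concern.** Whether the drug works better in one group than in another is a question about effect modification. For each dose there are four response rates (drug and placebo, high and low), and the quantity of interest is a difference of two differences. The assigned method stops one step short. Applied within each subgroup, it yields two drug-versus-placebo effects with their p-values and intervals, but nothing for the gap between them. Adding the signature as a further CMH stratum would not help, because CMH then averages the effect over high and low patients.

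Section 3.3.4 says the diagnostic biomarker assessments "aim to identify a biomarker that predicts response to GDC0853". It speaks of biomarkers in general and does not name the plasmablast signature, but this secondary objective is the protocol's most specific step in that direction. If only within-subgroup results are reported, the reader must set them side by side. How often that wrongly favours the high group depends on a true effect nobody knows, and nothing on the page shows how uncertain the high-versus-low gap is.

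**Working it through.** **Inputs.** From Section 6.1: 240 patients in a 1:1:1 ratio, so 80 per arm; placebo response 50%; improvement 25 points; subgroup prevalence 50%; subgroup level two-sided 0.20. Hence 80 × 0.5 = 40 per arm in each subgroup. Assumed here, because the documents do not say: placebo response is 50% in both subgroups, and the true effect in the low subgroup is varied.

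**The plan's own figures.** Exact Fisher power for 50% versus 75% is 88.3% with 80 per arm at 0.05, and 80.1% with 40 per arm at 0.20. Both stated values (88% and 80%) reproduce. The second is power for drug versus placebo inside one subgroup.

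**Precision of the missing contrast, per dose.** Let D = (drug − placebo in high) − (drug − placebo in low). Take 75% versus 50% in high and 50% versus 50% in low:

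- SE(D) = √[(0.75×0.25 + 0.5×0.5 + 0.5×0.5 + 0.5×0.5)/40] = √(0.9375/40) = 0.153
- 80% interval half-width = 1.2816 × 0.153 = 0.196
- 95% interval half-width = 1.960 × 0.153 = 0.300

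These are not adjusted for the randomization strata. With 30% or 70% prevalence the SE rises to about 0.17.

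**Power for D = 25 points at two-sided 0.20.** 0.25/0.1531 = 1.633, and 1.633 − 1.2816 = 0.351. The normal probability below 0.351 is about 0.637; adding 0.002 from the far tail gives 0.639. Simulation of the Wald test gives 0.658. By the formula, if the low group's effect is 10 points rather than 0, power falls to 40%; at 15 points it is 29%.

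**Illustration of side-by-side reading.** Suppose the true effect is the same in both subgroups. Let P be the chance that a Fisher test with 40 per arm at two-sided 0.20 favours drug. The chance of significance in high but not in low is then P(1 − P).

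| Common effect (points) | P | P(1 − P) |
|---|---|---|
| 0 | 0.073 | 0.068 |
| 5 | 0.157 | 0.132 |
| 10 | 0.287 | 0.205 |
| 15 | 0.457 | 0.248 |
| 20 | 0.639 | 0.231 |
| 25 | 0.801 | 0.160 |
| 30 | 0.914 | 0.078 |

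Over the same range, a direct test of D at two-sided 0.20 falsely favours high 10.1% to 11.1% of the time by simulation. With an uncorrected chi-square test in place of Fisher's, P(1 − P) is 23%, 25%, 21% and 12% at 10, 15, 20 and 25 points.

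**The other direction.** With a true 25 points in high and 0 in low, the side-by-side pattern appears with probability 0.801 × (1 − 0.073) = 0.742, against 0.64-0.66 for the direct test.

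**The case against.** The strongest reply is that the DAP may already contain this contrast. Section 6 sends the detail of all statistical methods there, and Section 6.4.2 does so again for the secondary analyses. A reader might infer that the interaction analysis is missing from the trial. The documents do not support that; they show only that the protocol assigns these endpoints a method that does not answer them and does not commit the DAP to one that does.

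Second, the comparison is named in advance and only its statistic is open. That is fair, and the high-minus-low difference and its SE could be obtained later by subtraction from two independent subgroup estimates. But the scale, the interval and the split into high and low would then be chosen after the fact.

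Third, the protocol has no rule that significance in high alone establishes the marker. A reader might infer from the table that it would draw that conclusion; it does not say so, and Section 6.4 treats positive tests as hypothesis generating. The table is therefore an illustration only, and it is mixed: side-by-side reading errs less often than the direct test at 0 and 30 points and picks up a true 25-versus-0 pattern more often.

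Fourth, naming the contrast does not by itself settle it. Sections 1.2.2, 6.1, 6.4 and 6.4.2 give no cut-point for high versus low, and the 50% prevalence is a power assumption. This objection stands, and the fix must include the cut-point.

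**Conclusion.** The mismatch between objective and assigned method is real and worth correcting. It is a gap in the specified analysis, not an arithmetic error. A reader might infer that the 80% power is wrong or is claimed for the high-versus-low question; neither is so, since Section 6.1 describes it as efficacy within a subgroup and the figure reproduces.

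The corresponding figures for the high-versus-low difference are weaker: SE about 15 points, 80% interval about ±20, 95% interval about ±30, and approximate power of 64-66% for 25 versus 0 points at two-sided 0.20. They assume 50% prevalence and 50% placebo response in both subgroups, ignore the strata, and for the power also assume no effect in the low group. In a hypothesis-generating Phase II study that imprecision is acceptable. It should be visible in the result, which requires the difference to be reported with its interval.

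**What to change.** In Section 6.4.2, for the two plasmablast endpoints, state that for each GDC-0853 dose the analysis will report the risk difference versus placebo in high-signature patients minus the risk difference versus placebo in low-signature patients, with 80% and 95% confidence intervals and a treatment-by-signature interaction test at two-sided 0.20. State that the high/low cut-point will be fixed before unblinding and that within-subgroup results are supportive. Apply the same wording to the two Week 24 exploratory plasmablast endpoints in Section 6.4.3. If the DAP already specifies this, a sentence in the protocol saying so is enough.

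A note in Section 6.1 and the synopsis that the 80% does not apply to the high-versus-low difference would be helpful but is optional.

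The cost is one extra estimate per dose and endpoint: 2 doses × 2 endpoints = 4, or 2 × 4 = 8 with the Week 24 endpoints. No patients, visits or data are added. The sponsor accepts a less favourable stated precision for the biomarker objective and, if the truth is 25 versus 0 points, flags the high group somewhat less often than by side-by-side reading (64-66% against 74%).

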### **6.4.3 Exploratory Efficacy Endpoints**

The exploratory efficacy endpoints are as follows:

- *SRI-5, 7, and 8 response at Weeks 24 and 48*
- *SRI-5-8 response at Week 48 with a sustained reduction of OCS dose to < 10 mg/day and ≤ Day 1 dose during Week 36 through Week 48*
- *SRI-5-8 response at Week 24 with a sustained reduction of OCS dose to < 10 mg/day and ≤ Day 1 dose during Week 12 through Week 24*
- Time to first SLE flare as defined by the SFI
- Time to first SLE flare as defined by the BILAG
- Total number of SLE flares as defined by the SFI
- Total number of SLE flares as defined by the BILAG
- *Reduction of ≥ 4 points from baseline in the SLEDAI-2K at Weeks 24 and 48*
- *SRI-4 response at Week 24 in patients with high plasmablast signature levels relative to patients with low levels*
- *SRI-4 response at Week 24 with a sustained reduction of OCS dose to < 10 mg/day and ≤ Day 1 dose during Week 12 through Week 24 in patients with high plasmablast signature levels relative to patients with low levels*
- Change in CLASI Total Activity Score at Week 24 and Week 48 relative to baseline
- ≥50% improvement in CLASI score in patients with at least moderate skin involvement (baseline CLASI ≥10)
- Change in SLICC/ACR Damage Index at Week 24 and Week 48 relative to baseline
- Change in joint involvement at Week 24 and Week 48 relative to baseline
- ≥50% improvement in swollen or tender joint count (28 joints) for patients with ≥8 swollen or tender joints at baseline
- Change in FACIT-Fatigue score at Week 24 and Week 48 relative to baseline
- Change in Patient's Global Assessment of disease activity at Week 24 and Week 48 relative to baseline
- Change in cumulative steroid dose use at Week 24 and Week 48 relative to baseline
- Glucocorticoid toxicity at Weeks 12, 24, 36, and 48 relative to baseline using the GTCI
- *Achieving* corticosteroid dose of < 10 mg/day among patients with a dose ≥ 10 mg/day at baseline

Exploratory endpoints will be evaluated for the ITT population. Time-to-event endpoints will be analyzed using the Kaplan-Meier methodology. Continuous endpoints will be analyzed using an appropriate analysis method, such as analysis of covariance, or

mixed-model repeated measures. Categorical endpoints will be analyzed using an appropriate statistical method, such as Cochran-Mantel-Haenszel or Fisher's exact test.

